### **Post-Procedure Pacing Guidelines**

- All patients should stay on telemetry until discharge
- Maintain temporary pacing until at least 48 hours post-implant in Cardiovascular Intensive Care Unit (CV-ICU) or local equivalent
- After 48 hours, obtain ECG and assess patient rhythm and conduction
- Based on assessment, and with the consult of an electrophysiologist as needed, take one of the following actions:
  - Discontinue temporary pacing
  - Continue temporary pacing for another 24 hours (longer if needed) to make further assessments
  - Place a permanent pacemaker according to ACC/AHA/HRS Guidelines for Device-Based Therapy of Cardiac Rhythm Abnormalities (Class I or IIb for Acquired Atrioventricular Block in Adults or Permanent Pacing in Chronic Bifascicular Block) as outlined in **Appendix R.13**
  - Prior to the permanent pacemaker implantation, document the reason for the placement of the permanent pacemaker via a 12-lead ECG
  - For complete heart block, review patient medications
  - Consider withholding some medications to assess for patient's intrinsic rate and conduction
  - If heart block persists off medications, a permanent pacemaker should be considered
  - If a permanent pacemaker is required, a dual chamber system is recommended to optimize patient hemodynamics
  - For additional information refer to the Pacing Guidelines in **Appendix R.13**

### **C.4.7.2 Surgical Aortic Valve Replacement**

#### **Minimum Standards for Surgical Aortic Valve Replacement**

Subjects randomized to SAVR should be treated according to the surgeon and hospital's standard practices. The surgeon or co-surgeon performing the SAVR must be a trial investigator for the site. The choice of surgical valve is left to the discretion of the investigator. **However, the use of a bioprosthetic valve is required.**

**SAVR must be conducted as an isolated procedure with exception of subjects that have been randomized to SAVR with revascularization (eg. Aortic replacement or Maze procedures are not permitted).** In cases of significant coronary artery disease that requires revascularization coronary artery bypass grafting (CABG) will be conducted concomitantly with SAVR.

Additional concomitant cardiac and non-cardiac procedures are not permitted with the exception of the procedures outlined under Additional Procedural Considerations.

#### **General Procedural Considerations**

One of the key requirements for good surgical outcome is an excellent collaboration of the dedicated multidisciplinary teams consisting of typically two cardiac surgeons with SAVR experience, a cardiac anesthesia team, an experienced cardio technician as well as at least two operation theater nurses.

#### **Operation Theater**

Surgical aortic valve replacement is to be performed in an operative theater with state-of-the-art technical equipment with certified sterility standards, adequate illumination, laminar flow, dedicated scrub nurses, and on site full technical support.

#### **Perfusion**

A dedicated, experienced perfusion team with greater than 75 Extracorporeal Circulation (ECC) runs per cardio technician per year who can perform all current cardioplegia strategies and is familiar with deep hypothermic circulatory arrest (DHCA) is recommended. The perfusion team should be capable of covering the full heart surgical spectrum including CABG, heart valve defect (HVD), Heart failure and assist devices, extracorporeal membrane oxygenation (ECMO) support, intra-aortic balloon pump (IABP), and cardiac transplant.

### **Pre-Procedure**

- Pre-medication recommendations:
  - Discontinue warfarin therapy 3 days prior to the procedure, if applicable
    - Confirm that the INR < 1.8 prior to the procedure
  - Administer antiplatelet therapy, per local standards
  - Consider adjunctive proton pump inhibitors, H2 receptor antagonists or antacids
- Routine Laboratory Tests:
  - Complete Blood Count
    - White Blood Count
    - Hematocrit
    - Hemoglobin
    - Platelet Count
  - Creatinine and Creatinine Clearance
    - If the GFR < 60 cc/min, consider:
      - Discontinuation of NSAIDs and ACE inhibitors
  - Cardiac Enzymes (CK/CK-MB)
  - International Normalized Ratio (INR), if applicable
  - Activated Partial Thromboplastin Time (aPTT)
  - B-type Natriuretic Peptide (BNP) or NT-proBNP
  - Liver Panel:
    - ALT
    - AST
    - Albumin
  - Sodium
  - Potassium
- 12-Lead Electrocardiogram
- One hour prior to the procedure, prophylactic antibiotic therapy of the Investigator's choice should be initiated:
  - Cefuroxime 750mg IV 1 hour pre-procedure, then 6 hours and 12 hours post-procedure
  - If allergic to Penicillin, prescribe Vancomycin 1g IV
  - Consider holding anti-hypertensives

### **Surgical Considerations**

Surgical aortic valve replacement is typically performed with cardio-pulmonary bypass (CPB) on an arrested heart with a clamped aorta. Local practice and surgical standards should govern type of cardioplegia and the temperature/flow/pressure perfusion strategy as well as the activated clotting time used at either institution for safe CPB. Typically a minimum of 2 liters/m^2/minute with a systemic arterial blood pressure of 60mmHg during CPB should be maintained and possibly increased in the elderly patients.

Cannulation for isolated SAVR CPB should be ascending aorta for arterial return unless there is ascending aortic arteriosclerosis or dilatation (>4cm in diameter), and right atrial for venous drainage. Embolic devices are not routinely used in SAVR.

**Typical surgical workflow and general procedural recommendations**

- *Procedural set-up and Anatomic Evaluation:*
  - The patient is prepared and draped
  - IV antibiotics should be administered following the local standard of care
  - Following the presternal skin incision the sternum is split
  - Prepare the mediastinum and open the pericardium
  - Inspect the ascending aorta for calcifications (including epiaortic scan if necessary)
  - Complete heparin application and arterial and venous cannulation
  - Initiate CPB, and at surgeons discretion, left heart venting via right upper pulmonary vein or pulmonary artery
  - Cross clamp the aorta and initiate cardioplegic arrest
  - Perform an aortotomy
  - Complete annular decalcification (the surgeon should take all possible means to prevent embolization of debris)
  
- *Prosthesis Specific Sizing:*
  - If the aortic annulus does not permit valve replacement with a patient matched valve diameter, the aortic annulus should be enlarged at the surgeon's discretion
  
- *Valve Preparation and Implantation:*
  - The valve prosthesis should be prepared following the manufacturer recommendations
  - After rinsing bioprosthetic valves should be kept wet throughout the procedure
  - Anchoring of the prosthesis with, for example, interrupted Teflon reinforced Tycron sutures or an equivalent technique is recommended
  - De-air and close the aortotomy
  - Insert temporary ventricular and atrial pacing wires and chest tubes
  - Wean from ECC hemostasis
  - Complete sternal wiring and layered closure
  
- *Additional Procedural Considerations:*
  - In case of concomitant significant subvalvular left ventricular outflow tract occlusion (LVOTO) then resection is recommended
  - If there is a significant patent foramen ovale (PFO) closure is recommended in cases of substantial right to left flow
  - It might be recommendable to apply CO2 surgical field flooding to ease de-airing
  
- *Intraoperative Aortic Assessment*
  - Transesophageal echo (TEE) is recommended in all cases to additionally assess for aortic calcifications before manipulating the aorta. In case of doubt an Epiaortic scan might further help for surgical decision making
  - Additionally the TEE should be used to assess for subvalvular LVOTO and patent foramen ovale
  
- *Before Termination of Surgery Repeat Intraoperative TEE*
  - TEE is recommended to assess the postoperative SAVR result
    - Assessment should include aortic valve function, central or paravalvular leakage, valve gradient, exclude remaining LVOTO from subvalvular stenosis as well as ventricular function with special emphasis on new segmental wall function abnormalities.
    - Any regurgitation of more than trace should be critically evaluated and at surgeon's discretion the valve re-inspected and if necessary changed.

### **Immediate Post-Procedure**

The procedure is considered complete at the time of skin closure. Immediately post-procedure the following tests and procedures must be performed and data collected:

- Cardiac Enzymes: CK within 8-12 hours post procedure and at any time when a clinical ischemic event is suspected.
  - CK-MB is required if CK is elevated >2X the laboratory upper limit of normal.
  - If a clinical event is confirmed, a total of 3 draws of cardiac enzymes within the first 24 hours (drawn approximately every 8 hours) following the clinical event should be obtained
- Concomitant Medications
- 12-lead Electrocardiogram (ECG) to be performed within 48 hours of procedure
- Abbreviated Neurological Assessment
  - National Institute of Health Stroke Scale (NIHSS) to be completed within 24 hours of procedure
- Transthoracic Echocardiogram (TTE)
  - Comprehensive transthoracic 2D echocardiogram (TTE) should be performed at least 24hours post-procedure but prior to discharge to assess device success (and no later than 7 days, whichever comes first)
  - Echocardiograms will be performed according to Echocardiography Procedures found in **Appendix R.7**
- Adverse Event review

### **Post-Procedural Medication**

- It is recommended that subjects are treated with aspirin (75-325mg daily) for a minimum of three months
- If warfarin therapy is indicated (eg. A-fib): maintain therapeutic anticoagulation with Heparin or Low Molecular Weight Heparin until INR between 2 and 3 is reached after loading with warfarin
- The preoperative antibiotic therapy may be repeated within the next 6 to 12 hours
- All patients should receive DVT prophylaxis with Heparin/LMWH starting approximately 6 hours after SAVR if bleeding permits
- Following the current recommendation all patients with prosthetic heart valves need endocarditis prophylaxis

### **Post-Procedure Pacing Guidelines**

- All patients should stay on telemetry until discharge
- Maintain temporary pacing until at least 48 hours post-implant in CV-ICU or local equivalent
- After 48 hours, obtain ECG and assess patient rhythm and conduction
- Based on assessment, and with the consult of an electrophysiologist as needed, take one of the following actions:
  - Discontinue temporary pacing
  - Continue temporary pacing for another 24 hours (longer if needed) to make further assessments
  - Place a permanent pacemaker according to ACC/AHA/HRS Guidelines for Device-Based Therapy of Cardiac Rhythm Abnormalities (Class I or IIb for Acquired Atrioventricular Block in Adults or Permanent Pacing in Chronic Bifascicular Block) as outlined in **Appendix R.13**
  - Prior to the permanent pacemaker implantation, document the reason for the placement of the permanent pacemaker via a 12-lead ECG
  - For complete heart block, review patient medications
  - Consider withholding some medications to assess for patient's intrinsic rate and conduction
  - If heart block persists off medications, a permanent pacemaker should be considered
  - If a permanent pacemaker is required, a dual chamber system is recommended to optimize patient hemodynamics
  - For additional information refer to the Pacing Guidelines in **Appendix R.13**

#### C.4.8 Assessments done at discharge (both SAVR and TAVI)

Prior to hospital discharge (or within 7 days post-index procedure, whichever occurs first) the following tests and procedures must be performed and data collected:

- Physical Examination
  - Vital signs
  - Major system findings
  - Skin Assessment – refer to Radiation Exposure and Data Collection, **Appendix R.23**
- Concomitant Medications
  - Use of relevant medications (diuretics, aspirin, anticoagulants, ACE-I, ARB, beta-blockers, statins and anti-platelets)
- Routine Laboratory Tests:
  - Complete Blood Count:
    - White Blood Count
    - Hematocrit
    - Hemoglobin
    - Platelet Count
  - Creatinine and Creatinine Clearance
  - Cardiac Enzymes (CK/CK-MB)
  - International Normalized Ratio (INR), if applicable
  - Activated Partial Thromboplastin Time (aPTT)
  - B-type Natriuretic Peptide (BNP) or NT-proBNP
  - Liver Panel:
    - ALT
    - AST
    - Albumin
  - Sodium
  - Potassium
- Neurological Assessments
  - National Institute of Health Stroke Scale (NIHSS)
  - Modified Rankin Score (mRS)
  - Mini-Mental State Exam (MMSE-2:SV)
  - Additional Neurological testing:
    - Visual Fields Testing
    - Gait Assessment
    - Hand Function
    - Writing Evaluation
    - Drawing Assessment
- Transthoracic Echocardiogram (TTE)
  - Comprehensive transthoracic 2D echocardiogram (TTE) should be performed at least 24hours post-procedure but prior to discharge to assess device success (and no later than 7 days, whichever comes first)
  - Echocardiograms will be performed according to Echocardiography Procedures found in **Appendix R.7**
- 12-lead Electrocardiogram
- Adverse Event review

#### C.4.9 Follow-Up Evaluations

All randomized subjects will undergo in-clinic follow-up evaluations at the following time points post implant.

All follow-up periods are defined as the number of days after the date of the index procedure (TAVI or SAVR).

##### Day 0 = day of index procedure (TAVI or SAVR):

- 30 days (- 7 days and + 14 days)
- 3 months (90 ± 14 days)
- 6 months (180 ± 30 days)
- 12 months (365 ± 30 days)
- 18 months (545 ± 60 days)
- 24 months (730 ± 60 days)
- 3 years (1080 ± 60 days)
- 4 years (1440 ± 60 days)
- 5 years (1800 ± 60 days)

All randomized subjects will complete long-term follow-up through at least 5 years. Based on clinical assessments or regulatory requirements, follow-up may be extended to up to 10 years post-index procedure. Upon completion of the final protocol visit (discontinuation) subject participation will be considered complete and the patient should then be followed per the local standard of care for their condition.

Note: For subjects where the Index Procedure is never attempted (eg. subject withdraws consent for the procedure but agrees to complete follow-up) follow-up intervals will be calculated from the 31st days post-randomization (i.e. the 1st day after the 30 day window from randomization to complete the Index Procedure).

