### C.3.5 *Number of Subjects*

Up to 2000 subjects will be randomized [1:1, TAVI: Surgical Aortic Valve Replacement (SAVR)]. The enrollment phase is anticipated to be approximately 36 months. Subjects will be followed through 5 years for assessment of long-term safety and efficacy endpoints. The total trial duration is expected to be approximately 8 years.

Enrollments shall not exceed 20% (approximately 400) of total randomized subjects at any individual site. Enrollment is competitive; therefore there is no set minimum number of subjects to be enrolled per site. Appropriate measures will be taken to monitor enrollment across geographies to ensure at least 40% of the total patient population is enrolled within the United States.

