### C.6.8 Secondary Endpoints

#### C.6.8.1 Secondary Endpoints Compared Between TAVI and SAVR

1. Incidence of Major Adverse Cardiovascular and Cerebrovascular Events (MACCE) at 30 days, 6 months, 12 months, 18 months, 24 months, and annually thereafter up to 5 years. MACCE is defined as a composite of:

- All-cause death
- Myocardial infarction (MI)
- All stroke, and
- Reintervention (defined as any cardiac surgery or percutaneous reintervention catheter procedure that repairs, otherwise alters or adjusts, or replaces a previously implanted valve)

MACCE-incidence estimates will be provided for the two treatment groups at 30 days, 6 months, 12 months, 18 months, 24 months, and annually thereafter up to 5 years. The statistical method will be the Bayesian version of a comparison of proportions (with predictions).

Additionally, incidence of MACCE will be compared at 30 days or hospital discharge, whichever is later. The statistical method will be the Bayesian version of a comparison of proportions.

2. The occurrence of individual MACCE components at 30 days, 6 months, 12 months, 18 months, 24 months, and annually thereafter up to 5 years.

MACCE components will be summarized and their incidence estimates provided at 30 days, 6 months, 12 months, 18 months, 24 months, and annually thereafter up to 5 years. The statistical method will be the Bayesian version of a comparison of proportions (with predictions).

3. Major Adverse Events (MAE) and individual components at 30 days, 6 months, 12 months, 18 months, 24 months, and annually thereafter up to 5 years.

MAE events and individual components will be summarized and the incidence of MAEs will be provided at 30 days, 6 months, 12 months, 18 months, 24 months, and annually thereafter up to 5 years. The statistical method will be the Bayesian version of a comparison of proportions (with predictions).

Additionally, incidence of major vascular complications and incidence of major or life-threatening bleeding events at 30 days or hospital discharge, whichever is longer, will also be compared using the Bayesian version of a comparison of proportions.

4. Incidence of Early safety at 30 days defined as a composite of:

- All-cause mortality
- All stroke (disabling and non-disabling)
- Life-threatening bleeding
- Acute kidney injury—Stage 2 or 3 (including renal replacement therapy)
- Coronary artery obstruction requiring intervention
- Major vascular complication

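### The final visit may fall up to 85 days before day 1825 and ends participation, so the promised follow-up through at least 5 years is not guaranteed

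*Combined protocol and SAP*

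**What the plan says.** Section C.4.9 counts follow-up in days from the index procedure, and C.6.1 repeats this for the analysis. The yearly targets start from "12 months (365 ± 30 days") and day 730 for 24 months, and then change to "3 years (1080 ± 60 days"), "4 years (1440 ± 60 days") and "5 years (1800 ± 60 days").

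On the length of follow-up, C.4.9 says "All randomized subjects will complete long-term follow-up through at least 5 years", and C.3.5 says "Subjects will be followed through 5 years for assessment of long-term safety and efficacy endpoints". On its end, C.4.9 says "Upon completion of the final protocol visit (discontinuation) subject participation will be considered complete". An extension to as long as 10 years is mentioned, but only as a possibility. C.4.19 describes the last visit as month 60 and returns subjects who have completed follow-up to local standard care.

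The 5-year time point is used in C.6.8.1. Its first endpoint, for example, is worded "Incidence of Major Adverse Cardiovascular and Cerebrovascular Events (MACCE) at 30 days, 6 months, 12 months, 18 months, 24 months, and annually thereafter up to", with year 5 as the end of the list. Most of the late event endpoints there are analysed by a Bayesian comparison of proportions that includes a prediction step.

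**The concern.** Early attendance at any visit but the last does no lasting harm, because the next visit covers the interval. Nothing that the plan requires follows the 5-year visit. A subject may therefore attend within window on day 1740, complete the trial, and have an event on day 1800 that no scheduled contact would record. Another subject with an event on the same day who had not yet attended would be counted.

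Without a stated counting rule, classification near 5 years can depend on the appointment date. What is at stake is complete ascertainment for the long-term secondary event endpoints. Once subjects have exited, the missing days may not be recoverable.

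**Working it through.** **Inputs.** Visit days and windows come from C.4.9. The assumed 24-month rate of death or disabling stroke, 17%, comes from the sample size justification in C.6.5.2. It serves here only to size the gap. The documents give no distribution of visit times, so those below are assumptions.

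**1. Reproduce the targets.** Day 1800 is 5 × 360, or 60 months × 30 days, which agrees with the month 60 of C.4.19. It does not follow from the year length used at 12 and 24 months.

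| Visit | Target day | Days per year | 365-day year | Difference |
|---|---|---|---|---|
| 12 months | 365 | 365 | 365 | 0 |
| 24 months | 730 | 365 | 730 | 0 |
| 3 years | 1080 | 360 | 1095 | −15 |
| 4 years | 1440 | 360 | 1460 | −20 |
| 5 years | 1800 | 360 | 1825 | −25 |

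**2. Shortfall at the last visit.** The window is 1800 − 60 = 1740 to 1800 + 60 = 1860, which is 121 days.
- At the target: 1825 − 1800 = 25 days (25/1825 = 1.4%).
- At the earliest permitted visit: 1825 − 1740 = 85 days (85/1825 = 4.7%).
- Window days before day 1825: 85 of 121 = 70%. The other 36 (30%) fall on or after it.
- If 5 years is read as day 1800 instead, the earliest visit is still 1800 − 1740 = 60 days short.

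**3. Share of event-free subjects who exit before day 1825.** With visits spread evenly over the window, the share is 70%. With visits normal around mean m and standard deviation s, it is Φ((1825 − m)/s):
- m = 1800: 80% (s = 30), 89% (s = 20), 95% (s = 15).
- m = 1815: 63 to 75% (s = 30 to 15).
- m = 1825: 50%.
- m = 1840: 31% (s = 30) to 16% (s = 15).

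**4. Effect on a 5-year incidence.** Assume a constant hazard fitted to 17% at day 730: h = −ln(1 − 0.17)/730 = 0.000255 per day. The cumulative incidence at day t is 1 − exp(−h·t):
- day 1740: 35.9%
- day 1800: 36.8%
- day 1825: 37.2%

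If every event-free subject were last seen at the target and then counted as event-free, the rate would be low by 37.2 − 36.8 = 0.4 points. If all were last seen on the earliest day, it would be low by 37.2 − 35.9, about 1.4 points before rounding.

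**5. Would moving the target be enough?** A target of day 1825 with the same ±60 gives days 1765 to 1885, and 60 of those 121 days (50%) still precede day 1825. The window or the exit rule must change as well.

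**The case against.** The strongest reply is that day 1825 is brought in from outside. The protocol defines follow-up in days and equates 5 years with 1800 ± 60. Month 60 in C.4.19 fits 30-day months, as do the 90- and 180-day targets at 3 and 6 months. No text available to me ties a 5-year rate to day 1825. That stands as a defence of the target. It does not rescue the window, because a final visit on day 1740 precedes day 1800 too and so conflicts with the commitment to at least 5 years under either definition. The contact rule for missed visits (C.4.15) operates inside the visit window, and the extension beyond 5 years is optional, so neither closes the gap.

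A reader might go further and infer three things that the documents do not support:
- **That most subjects leave before 5 years.** This depends on visit timing, which the plan does not give. A compliant final visit can fall as late as day 1860.
- **That the 5-year rates are not delivered.** The method includes predictions, and the section to which its details are referred (C.11) is not in the text available to me. The one denominator spelled out, for index-procedure events at 30 days, is visit-based: subjects evaluated at that visit or later, plus those not evaluated who had an event. A similar rule at 5 years would reduce the problem.
- **That every secondary event endpoint is affected.** Early safety, peri-procedural neurological injury and index-procedure events are all assessed by 30 days.

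It is also fair to say that the schedule is the same in both arms, so little bias in the treatment difference is to be expected.

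**Conclusion.** The point holds as a minor inconsistency. Section C.4.9 changes year length after 24 months and ends participation at a visit permitted from day 1740, so it does not guarantee the follow-up that it promises. This part rests on the protocol's dates alone.

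The size rests on assumptions. About 70 to 89% of event-free subjects would exit before day 1825 if visits are even over the window or centred on day 1800 with a standard deviation of 20 to 30 days. The share is much lower if sites schedule late. The effect of 0.4 to 1.4 points assumes a constant hazard taken from the primary composite and the least favourable counting rule. Endpoints with another late hazard would differ.

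The reach is limited to secondary event endpoints reported annually to 5 years, such as MACCE, MAE, strokes and cardiovascular deaths. The primary endpoint is at 24 months, and no test in C.6.10.1 uses a time point later than 24 months. The sample size is unaffected. The short 3- and 4-year targets are untidy but not harmful in themselves, because a later visit follows.

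**What to change.** In C.4.9, set the 3-, 4- and 5-year visits at days 1095, 1460 and 1825. Then do one of the following:
- make the final window one-sided (day 1825, −0/+60); or
- keep a two-sided visit window and require a vital-status and event contact on or after day 1825 before the Study Exit eCRF is completed.

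Align the ±60 echocardiography window in Appendix R.7 and the month-60 wording in C.4.19. State in the SAP which day counts as 5 years, and how event-free subjects last seen before that day are counted.

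The cost is three visit days and one window or contact rule, through a protocol amendment. The target for the last visit moves 25 days later, or each subject last seen early receives one phone call. A one-sided window also shrinks from 121 to 61 days, so somewhat more out-of-window visits are possible; the contact option avoids this. The change must be in force before subjects reach their final visits.
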